5.4. Study Rationale

The purpose of this study is to assess the systemic bioavailability of diclofenac in the presence and absence of capsaicin.

Capsaicin has been shown to act as a penetration enhancer (e.g., for indomethacin [6], naproxen [7]) and thus, might improve the penetration rate and absorption of diclofenac. In addition, both substances have different pharmacodynamics properties and complementary mechanisms of action. By combining both substances in a topical formulation, the new combination product will lead to an increased pain relief compared to the respective mono products.

For a more detailed description of the drug profile refer to the current IB [5], which is included in the ISF.

The proposed study in healthy males and females is designed to establish a PK profile for the topically applied test and reference products to evaluate relative bioavailability.

There is some evidence of racial differences in the transcutaneous penetration of chemicals and drug absorption: decreased transcutaneous penetration has been reported in Black people [13]. To take this into account the study population will be stratified 50:50, Caucasian versus Black people. This will allow estimating and comparing PK endpoints by treatment and race. However, bioavailability ratios as intra-individual comparisons are not expected to be influenced by race. To confirm this, a supportive analysis is planned including the stratification factor race in the model.

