6. STUDY OBJECTIVES

The main objective of this study is to assess the relative systemic bioavailability of diclofenac in the presence and absence of capsaicin by comparing the systemic bioavailability of diclofenac from a combination product (Diclofenac 2% + Capsaicin 0.075% Topical Gel) with two diclofenac only products, Diclofenac Mono Gel 2% and Voltarol® 12 Hour Emulgel 2.32% Gel, following topical administration. A [REDACTED]

[REDACTED]

[REDACTED]

In order to examine potential racial differences in pharmacokinetics (PK), the study population will be stratified 50:50, Caucasian versus Black people. With respect to the main objective, additionally a supportive analysis will be performed to investigate the influence of race on the intra-individual bioavailability ratios.

Refer to [Section 11.4](#) and [Section 9](#) for primary and secondary endpoints/variables.

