11.2. Determination of Sample Size

Up to 48 eligible subjects will be entered into the study to complete the study with at least 42 evaluable subjects.

The sample size determination is not based on a power calculation, but to assure a precise estimation of relative bioavailability ratios with respect to AUC_{ss} and $C_{max,ss}$. Precision is defined as the ratio of upper to lower confidence interval (CI) limit and can also be shown in terms of the width of CIs (note that the precision is independent of the actual ratio of geometric means [gMeans] but CIs are not as can be seen in the table below).

Different estimates of the geometric coefficient of variation (gCV) for AUC and C_{max} values of topical diclofenac were found in literature [9] regarding AUC_{ss} and $C_{max,ss}$ of PENNSAID topical solution and [10] regarding C_{max} and AUC_{0-24} of Voltaren topical gel. There, variability was very high, gCVs were calculated from CIs of ratios which ranged from 21 to

41 % and even 57% in one case. Based on this data, a gCV of 40% was used for estimation of precision for different scenarios.

Assuming an intra-individual variability of 40% for both AUC_{ss} and $C_{max,ss}$, the trial will need N=42 analyzable subjects in order to achieve two-sided 90% CIs meeting a precision of 1.42 with a probability of 95%.

Table 11-1 Expected Two-sided 90% Confidence Intervals for Different Ratios T/R and gCVs for a Sample Size of 42, Coverage Probability = 95%

gCV [%]	T/R	90% CI	Precision upper CL/lower CL
40	0.95	80 - 113	1.41
	1.00	84 - 119	1.42
	1.05	88 - 125	1.42
45	0.95	78 - 115	1.47
	1.00	83 - 121	1.46
	1.05	87 - 127	1.46

The calculation was performed as described by Julious [11, Section 7.2] and Elashoff [12].

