11.7. Analysis of Relative Bioavailability

Relative bioavailability will be estimated for diclofenac by the ratios of the gMeans (test/reference [T/R]) for AUC and C_{max} at steady state (refer to [Section 11.4.1](#)). Additionally, their two-sided 90% CIs will be provided.

The statistical model will be an analysis of variance (ANOVA) on the logarithmic scale including fixed effects for sequence, subject nested within sequence, period and treatment. For each endpoint, the difference between the expected means for log(T)-log(R) will be estimated by the difference in the corresponding adjusted means (Least Squares Means). CIs

* SAS® Version 9.2 or higher of the SAS System. Copyright© 2002-2003. SAS Institute Inc. SAS and all other SAS Institute Inc. product or service names are registered trademarks or trademarks of SAS Institute Inc., Cary, North Carolina, USA.

will be calculated based on the residual error from ANOVA. The differences between the test and reference product and the CIs will be back-transformed to the original scale, resulting in point estimates of the T/R gMean ratios and 90% CIs.

The following comparisons will apply:

- Test Product 2 vs Reference
- Test Product 2 vs Test Product 1

Only the data for the comparison under investigation will be included in the statistical analysis (i.e., when comparing Test Product 2 and Reference, the data for the Test Product 1 will be removed from the dataset), only subjects with data for both products will be retained in the analysis.

[REDACTED]

The effect of race on relative bioavailability will be analyzed as supportive analysis, supportive because race is not expected to influence intra-individual bioavailability ratios [14].

The statistical model of the supportive analysis will be an ANOVA on the logarithmic scale including fixed effects for sequence, period, race, treatment, treatment and race interaction and subject nested within sequence and race interaction. The effect of race will be checked

and for each endpoint, least squares means by treatment and race will be tabulated. Point estimates of the T/R gMean ratios and 90% CIs will be presented by race in the same way as for the main analysis.

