6.3.3 Statistical Significance Level

All statistical tests will be two-sided and will be performed at the 5% level of significance, unless otherwise stated. All CI will be two-sided 90% Confidence intervals.

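### The race analysis is said to confirm that race does not affect the bioavailability ratios, but the protocol names no race-to-race contrast, and that contrast's expected 90% CI is about 0.75 to 1.33

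*Protocol*

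**What the plan says.** Protocol 5.4 reports evidence of lower skin penetration in Black people and stratifies 50:50 by race so that PK endpoints can be compared by treatment and race. It then says that the within-subject ratios are not expected to depend on race, and continues: "To confirm this, a supportive analysis is planned including the stratification factor race in the model". The objectives (section 6, and the synopsis) are milder; there the supportive analysis is "to investigate the influence of race on the intra-individual bioavailability ratios".

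Section 11.7 fits an ANOVA on the log scale that includes race and a treatment-by-race term. It says that the effect of race will be checked, that least squares means by treatment and race will be tabulated, and that "Point estimates of the T/R gMean ratios and 90% CIs will be presented by race in the same way as for the main analysis". It names no estimate or interval for the difference between the races' ratios, no margin, and no criterion for confirmation.

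The sample size concerns the overall ratios only: "The sample size determination is not based on a power calculation, but to assure a precise estimation of relative bioavailability ratios" (11.2). SAP 6.3.3 sets a general rule: "All statistical tests will be two-sided and will be performed at the 5% level of significance, unless otherwise stated". The SAP's own description of the race analysis is redacted. The SAP addendum shows that race tables exist, but not what they contain.

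**The concern.** Whether race influences T/R is a question about the difference between two log ratios, that is, about the treatment-by-race contrast. Two by-race intervals shown side by side do not display that difference. A non-significant interaction shows absence of influence only if the contrast is estimated precisely enough to exclude differences that matter.

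The question has some substance. Section 5.4 also describes capsaicin as a possible penetration enhancer. A within-subject comparison cancels a race effect common to both products, but it does not cancel an enhancer effect that depends on the skin barrier. (This mechanism is an inference; the protocol does not state it.) What is at stake is whether the report could call the expectation confirmed when the data leave a sizeable race difference open.

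**Working it through.** **Inputs.** Two-sided 90% CIs ("Additionally, their two-sided 90% CIs will be provided", 11.7). Planning variability (11.2): "Based on this data, a gCV of 40% was used for estimation of precision for different scenarios"; the literature values cited there run from 21 to 41%, once 57%, and Table 11-1 also uses 45%. At least 42 evaluable of up to 48 subjects (11.2), with 4 per race in each of 6 sequences (8.3). This gives 24 per race enrolled and about 21 per race if 42 are evaluable. Each comparison uses only the data of its two products (11.7).

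**The plan's own figure.** "Precision is defined as the ratio of upper to lower confidence interval (CI) limit" (11.2).
- σw = √ln(1 + 0.40²) = √0.1484 = 0.385
- log half-width = t(0.95; 40) · σw · √(2/42) · √(χ²(0.95; 40)/40) = 1.684 × 0.385 × 0.218 × 1.181 = 0.167
- limits at T/R = 1.00: 84.6 to 118.2; unrounded precision 1.397

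Rounding the limits outward gives 84 to 119, and 119/84 = 1.42, as stated. The same rule reproduces all six rows of Table 11-1, so the inputs are read as the plan intends.

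**By-race ratio, 21 per race.** Within-subject degrees of freedom: 42 − 1 (treatment) − 2 (periods) − 1 (interaction) = 38.
- SE = √(2 × 0.1484/21) = 0.119
- half-width = 1.686 × 0.119 = 0.200; 90% CI around 1.00: 0.82 to 1.22

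Two such intervals still overlap until the races' ratios differ by a factor of exp(2 × 0.200) = 1.49.

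**Ratio of ratios, 21 per race.**
- SE = √(2 × 2 × 0.1484/21) = 0.168, twice the 0.084 of the overall ratio
- half-width = 1.686 × 0.168 = 0.2835; 90% CI around 1.00: 0.75 to 1.33
- expected precision exp(2 × 0.2835) = 1.76, or 1.96 with the plan's 95% probability, against 1.42 for the overall ratio

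With 24 per race (df 44) the interval is 0.77 to 1.30.

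**Interaction test, if made at two-sided 5%.** Significance needs an observed ratio of ratios above exp(2.024 × 0.168) = 1.41. Power is from the noncentral t with df 38 and noncentrality ln(true ratio)/SE. At 40%, 80% power needs a true ratio of about 1.62.

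| gCV | 90% CI around 1.00 | Power at 1.25 | Power at 1.5 |
|---|---|---|---|
| 21% | 0.86 to 1.17 | 67% | 99% |
| 40% | 0.75 to 1.33 | 25% | 65% |
| 45% | 0.73 to 1.37 | 21% | 56% |
| 57% | 0.68 to 1.48 | 16% | 40% |

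(21 per race throughout.)

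**If confirming meant a 90% CI within 0.80 to 1.25.** This margin is an assumption; the documents give none. At true equality, the chance of meeting it with 21 per race is about 0.2% at a gCV of 40% (0.5% with 24 per race) and 56% at 21%. At 40%, about 103 per race would be needed for 80%.

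**The case against.** The strongest reply is that little depends on this. The analysis is labelled supportive, the word at issue stands in a rationale section, the objectives and methods use milder verbs, and the sample size claims nothing about race. That stands, and it limits the weight of the point.

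Second, the planned model contains the interaction, and its coefficient is the log ratio of ratios. With equal groups and a common residual, a reader could also rebuild the interval from the by-race output: 0.200 × √2 = 0.2835. This stands in part. The quantity is estimable and may be looked at when the race effect is checked. But a stated aim should not depend on readers reconstructing its result, and what they would see directly is the overlap of two intervals.

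Third, a reader might make stronger inferences that the documents do not support:
- *That the 50:50 stratification exists for the ratio question.* Sections 5.4 and 6 tie it to racial differences in PK; the ratio question is additional.
- *That a non-significant interaction or overlapping intervals will be taken as confirmation.* No visible text sets such a rule or explicitly prescribes an interaction test, and the 5% level is a general default.
- *That the SAP omits the contrast.* Its race section is redacted, so no omission can be alleged.
- *That this design could never support the expectation.* At the lowest cited gCV the interval is 0.86 to 1.17, and whether that would suffice depends on a margin nobody has set.

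**Conclusion.** The point holds as a mismatch between stated aim and visible output. Section 5.4 promises confirmation, while the protocol sets no criterion for it and does not name the contrast that bears on it. At the planning gCV, results compatible with a race difference of about a quarter to a third in either direction are to be expected even if the ratios are truly equal. Such data would not contradict the expectation, but they would not confirm it either.

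The size rests on a gCV of 40%, 21 evaluable subjects per race, a residual variance common to both races, and balanced sequences. Having 24 per race changes little, and the higher cited gCVs make the interval wider. The power figures apply only if the interaction is tested at 5%. The main comparisons of Test 2 with the reference and with Test 1 are not touched, and the sample size needs no change.

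**What to change.** In protocol 11.7, add the treatment-by-race contrast to the supportive output. Report it back-transformed as a ratio of ratios with its 90% CI, for Test 2 versus reference (B/C) and Test 2 versus Test 1 (B/A), for each primary endpoint. Make the same addition to the SAP race analysis if the redacted text does not already contain it.

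In 5.4, replace *To confirm this* with *To estimate this* or *To investigate this*, in line with section 6. State the expected interval of about 0.75 to 1.33 at a gCV of 40% with 21 per race, ideally with the range across the cited gCVs.

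The cost is one ESTIMATE statement per comparison in a model that is already planned, one table line and a wording change. No further subjects are needed for this. Matching the overall ratio's precision would take about four times as many (4 × 42 = 168, or 84 per race), which a supportive question does not justify. The downside for the sponsor is a less favourable claim about race.

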5.5. Risks and Benefits

Safety measures are instituted to closely monitor subject safety during this clinical study and to assess known risks of the investigational medicinal products (IMPs).

As healthy male and female subjects will be included in this clinical study, they will not directly benefit from participation.

6. STUDY OBJECTIVES

The main objective of this study is to assess the relative systemic bioavailability of diclofenac in the presence and absence of capsaicin by comparing the systemic bioavailability of diclofenac from a combination product (Diclofenac 2% + Capsaicin 0.075% Topical Gel) with two diclofenac only products, Diclofenac Mono Gel 2% and Voltarol® 12 Hour Emulgel 2.32% Gel, following topical administration. A [REDACTED]

[REDACTED]

[REDACTED]

In order to examine potential racial differences in pharmacokinetics (PK), the study population will be stratified 50:50, Caucasian versus Black people. With respect to the main objective, additionally a supportive analysis will be performed to investigate the influence of race on the intra-individual bioavailability ratios.

Refer to [Section 11.4](#) and [Section 9](#) for primary and secondary endpoints/variables.

7. INVESTIGATIONAL PLAN

Bias is limited by strict adherence to the inclusion and exclusion criteria, the use of a randomization schedule and application of the particular study design. All measurement procedures are clearly defined in advance, and consistently and precisely applied.

7.1. Overall Study Design and Plan: Description

7.1.1. Study Design

This will be a multiple-dose, open-label, randomized, 3-period, 3-treatment, 6 sequence (3x3x6) crossover study with topically administered diclofenac 2% (2 g) in the presence and absence of capsaicin 0.075%, in at least 42 healthy male and female subjects (stratified 50:50 Caucasian versus Black people) in a single study center.

The study will comprise:

- Screening period of maximum 21 days.
- Three-treatment periods (each of which will include a multiple-dose period of 7 days [twice daily and only in the morning on Day 7] and two PK profile periods of 12 hours [Day 1] and 24 hours [Day 7]) separated by a wash out period of at least 7 calendar days between the last administration of the IMP in a treatment period and the first administration of IMP in the next treatment period. Clinic stay/visits will be as follows:
 - Subjects will be admitted to the study center on Day -1 and leave the center after the morning dose on Day 2, at least 24 hours after the initial dosing on Day 1
 - Subjects will visit the study center on Days 3 and 4 for the morning dose
 - On Day 5, they will visit the center for PK blood sampling prior to morning and evening dose and will be re-admitted to the study center on the evening of Day 5
 - Subjects will leave the center at least 24 hours after the morning dose on Day 7
- A follow-up visit will occur within 72 hours after completion of the last treatment period of the study.

Before the first administration of IMPs subjects will be randomized to one of 6 treatment sequences stratified by race (Black, Caucasian), i.e., 4 Black and 4 Caucasian subjects will be assigned to each treatment sequence.

7.2. Discussion of Study Design

7.2.1. Treatment Periods and Schedule of Study Assessments

The timing of assessments is displayed in [Table 7-1](#).

The time of dosing commencement may vary for logistical reasons. Actual clock times will vary between subjects, in relation to actual dosing times.

Boehringer Ingelheim Pharma GmbH & Co. KG
Combination of Diclofenac 2% + Capsaicin 0.075%**Table 7-1 Schedule of Study Assessments**

Assessment	Screening (Day -21 to -1)	Admission	Treatment Period 1				Admission	Treatment Period 2			Admission	Treatment Period 3			Follow-up Visit ¹
		Days -1 & 5	Days 2 - 4	Day 5, 6	Days 1 & 7	Days -1 & 5	Days 2 - 4	Day 5, 6	Days 1 & 7	Days -1 & 5	Days 2 - 4	Day 5, 6	Days 1 & 7		
Informed consent	X														
In-house stay ²		X			X	X			X	X			X		
Demographic and anthropometric data ³	X														
Review of inclusion/exclusion criteria	X														
Alcohol and tobacco consumption patterns	X														
Medical and medications history ⁴	X	X													
Adverse events and concomitant medication ⁵	X	X	X	X	X	X	X	X	X	X	X	X	X	X	
Physical examination ⁶	X														
Vital signs ⁷	X				X				X				X	X	
12-Lead ECG ⁸	X													X	
Hematology ⁹	X													X	
Clinical chemistry ¹⁰	X													X	
Serology tests ¹¹	X														
Urinalysis ¹²	X														
Pregnancy test ¹³ (female subjects only)	X	X				X				X				X	
Urine screen for drugs of abuse ¹⁴	X	X				X				X					
Urine screen for tobacco use ¹⁵	X														
Alcohol breath test ¹⁶	X	X				X				X					

Boehringer Ingelheim Pharma GmbH & Co. KG
Combination of Diclofenac 2% + Capsaicin 0.075%

Assessment	Screening (Day -21 to -1)	Admission	Treatment period 1				Admission	Treatment period 2			Admission	Treatment period 3			Follow-up Visit ¹
		Days -1 & 5	Days 2 - 4	Day 5, 6	Days 1 & 7	Days -1 & 5	Days 2 - 4	Day 5, 6	Days 1 & 7	Days -1 & 5	Days 2 - 4	Day 5, 6	Days 1 & 7		
Randomization					X (Day 1)										
Weighing of the IMP tube ¹⁷		X	X	X	X	X	X	X	X	X	X	X	X		
██████████		X	X	X	X	X	X	X	X	X	X	X	X	X	
IMP administration ¹⁹		X ¹⁸	X				X ¹⁸	X			X ¹⁸	X			
PK profile ²⁰					X				X				X		
Additional PK sampling ²¹		X		X		X		X		X		X			
Inspection of IMP application sites by PI ²²	X	X	X	X	X	X	X	X	X	X	X	X	X		
Overall assessment of tolerability ²³					X (Day 8)				X (Day 8)				X (Day 8)		

ECG = electrocardiogram; IMP = investigational medicinal product; PK = pharmacokinetic

1. Within 72 hours of completion of the last period of the study or, in the case of a subject who took the IMP and was withdrawn or withdrew, within 72 hours of withdrawal/withdrawing from the study.
2. Subjects will be admitted to the study center on Day -1 and the evening of Day 5 and will be discharged after the morning dose on Day 2 and at least 24 hours after last dosing on Day 7.
3. Sex, race, date of birth, age, height and body weight.
4. The recorded medical history will be updated if necessary on admission to treatment period 1.
5. Medication taken before dosing will be entered as history in the screening CRF of the subject.
6. A full physical examination will include the following: Evaluation for jaundice, pallor (anemia), cyanosis, clubbing, edema and lymphadenopathy; skin evaluation; external ophthalmological evaluation, including funduscopy; ear, nose and throat; cardiovascular assessment; respiratory assessment; abdominal evaluation; musculoskeletal assessment and neurological assessment; other evaluations may be performed as deemed necessary by the Investigator. This will be commented upon in the clinical study report, if applicable. Refer to [Section 7.2.7](#) for follow-up physical examination.
7. Supine and standing systolic and diastolic blood pressure and pulse will be recorded at screening and at the follow-up visit. Supine blood pressure and pulse will be recorded before administration of IMP; in addition, supine blood pressure and pulse will be recorded at 2, 4 and 6 hours post-dose (Days 1 and 7). Body temperature will be recorded at screening and before administration of IMP (morning dose).

8. Standard 12-lead ECG will be performed at screening and at the follow-up visit.
 9. Hematology (ethylenediaminetetraacetic acid [EDTA tubes]): white blood cell count, red blood cell count, hemoglobin, hematocrit, mean corpuscular volume, mean corpuscular hemoglobin, mean corpuscular hemoglobin concentration, absolute differential count (neutrophils, lymphocytes, monocytes, eosinophils and basophils) and platelets.
 10. Clinical chemistry (Serum separator tubes [SST]): Potassium, sodium, urea, creatinine, uric acid, calcium, protein, albumin, total bilirubin, alkaline phosphatase (ALP), gamma glutamyl transferase (GGT), aspartate aminotransferase (AST), alanine aminotransferase (ALT) and glucose.
 11. Tests for human immunodeficiency virus (HIV), Hepatitis B and Hepatitis C, performed using commercially available test kits. Pre- and post-test counseling will be provided as appropriate.
 12. Urinalysis (dipstick): Glucose, bilirubin, ketone, specific gravity, blood, pH, protein, urobilinogen, nitrite and leucocytes. Abnormal urinalysis results may be repeated at the discretion of the Investigator. All results will be reported.
 13. Serum pregnancy test (quantitative β -HCG [beta human chorionic gonadotropin] method) at screening. On admission to each treatment period (Day -1 each period) urine pregnancy testing will be performed. If any of these tests are positive, subjects will not be allowed further participation in the study. Urine pregnancy test at the follow-up visit.
 14. Using a rapid, one-step screening test for simultaneous, qualitative detection of multiple drugs and drug metabolites, such as amphetamines, barbiturates, benzodiazepines, cocaine, opiates, phencyclidine (phenylcyclohexylpiperidine), tetrahydrocannabinol, methadone, methamphetamine, tricyclic antidepressants, oxycodone and propoxyphene. Subjects with alleged false positive test results will be excluded from the study. However, a positive test may be repeated once at the discretion of the Investigator.
 15. Cotinine testing using commercially available testing procedures.
 16. Alcohol breath test using a portable breath alcohol measuring device. The test will be performed at screening, on admission to each treatment period and at random. If any of these tests are positive, subjects will not be allowed further participation in the study.
 17. The tubes will be weighed before and after dosing, whenever the subject is at the study center.
- [REDACTED]
19. IMP will be self-administered in the morning and evening (12 hours apart) on Days 1 to 6 and only in the morning on Day 7. Refer to [Section 7.2.6](#) for window allowance.
 20. Blood for PK analysis will be collected on Day 1 at the following time points: 0 hours (prior to morning dose) and at 0.5, 1, 2, 3, 4, 6, 8, 10 and 12 hours post-dose (prior to evening dose) (total: 10 samples per treatment period) and on Day 7 pre-dose at 0 hours and at 0.5, 1, 2, 3, 4, 6, 8, 10, 12, 14, 16, 18, 20 and 24 hours post-dose (15 samples per treatment period). PK sampling should take preference over other assessments.
 21. Additional blood samples to establish attainment of steady state will be collected on Days 5 and 6 (prior to morning dose and evening dose).
 22. Inspection of IMP application sites will be done at screening, before every IMP administration and post-dose at 1 and 6 (\pm 9) hours on Day 1 and Day 7, respectively. On Days 2 to 5 inspections will be done before IMP administration during the morning visit to the clinic (subjects will still be in the clinic the morning of Day 2) and on Day 6 inspection will be done before IMP administration, in the morning and evening, respectively.

23. Assessment will be done before discharge on the morning of Day 8. Refer to [Section 9.1.2](#) and [Appendix 15.2](#).

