7.3.3. Withdrawal Criteria

Subjects have the right to withdraw from the study at any time, irrespective of the reason, without detriment to their medical care.

The following are pre-defined incidents that may lead to withdrawal from further participation at the discretion of the PI, and are optional withdrawal criteria:

1. AEs at the discretion of the PI.
2. Intercurrent illness requiring medication. The decision whether or not to withdraw the subject will be at the discretion of the PI and will depend on the nature of the illness and medication used.
3. Protocol violation by subjects, at the discretion of the PI. Protocol violation is defined as the willful disobeying of protocol instructions which have been communicated to the subjects verbally and in writing.

The following are pre-defined incidents that will lead to withdrawal from further participation and are mandatory withdrawal criteria:

4. Pathologically raised oral body temperature, above 38.0°C, before morning dose of IMP administration on profile days.
5. Positive testing for pregnancy during the study.
6. Positive testing for drugs of abuse during the study.
7. Positive alcohol breath test during the study.
8. Skin irritation of such magnitude that dosing is not possible at IMP application site of the marked thigh during a specific period (the other thigh may be used in another period if needed).
9. If the subject withdraws consent.

The primary reason for treatment discontinuation will be documented (see Source Document Agreement).

If the PI withdraws a subject from treatment or if a subject declines further participation, a follow-up visit will be completed for those who were exposed to IMP, within 72 hours of withdrawal/withdrawing from the study.

If a subject's reason for discontinuation is an AE, this must be reported in accordance with the procedures detailed in [Section 12](#). The Investigator must make every effort to contact a subject before he/she can be regarded as lost to follow-up.

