6.1.2.7 Overall Assessment of Tolerability

The patient will assess the overall tolerability of the trial treatment on a 4-point verbal rating scale by answering the question: "How would you rate the overall tolerability of the study medication?" (0 = poor; 1 = fair; 2 = good; 3 = very good). The Investigator should make the corresponding assessment at about the same time as the patient. Assessments should be made independently from each other, i.e.,

[Redacted] International
Statistical Analysis Plan

without knowing the other's assessment result when making the assessment. Assessments will be performed according to the schedule in section 11.

6.1.2.8 *Inspection of IMP application sites*

Inspection of IMP application sites will be done at screening, before every IMP administration and post-dose at 1 and 6 (± 9) hours on Day 1 and Day 7, respectively. On Days 2 to 5 inspections will be done before IMP administration during the morning visit to the clinic (subjects will still be in the clinic the morning of Day 2) and on Day 6 inspection will be done before IMP administration, in the morning and evening, respectively.

6.1.2.9 *Concomitant Medication*

Concomitant medication will be coded using the World Health Organisation-Drug Dictionary (WHO-DD) (Version WHODDE MAR 2017) and will be classified by Anatomical Therapeutic Chemical (ATC) categories.

6.1.3 *Pharmacokinetics Variables*

6.1.3.1 *Pharmacokinetic Parameters*

Unless otherwise stated, derivation of pharmacokinetic (PK) parameters will be the responsibility of Quantitative Clinical Development (QCD), [Redacted] International. The following PK parameters will be determined for diclofenac in plasma following single dose administration:

[Redacted]

[Redacted]	[Redacted]
[Redacted]	[Redacted]
[Redacted]	[Redacted]

[REDACTED] International
Statistical Analysis Plan

The following pharmacokinetic (PK) parameters will be calculated for Diclofenac in plasma following multiple dose administration:

Table 4 PK Parameters after Multiple Dose Administration for Diclofenac

Parameter	Definition
[REDACTED]	[REDACTED]
$C_{max,ss}$	[1] Maximum observed concentration at steady state (Day 7)
$t_{max,ss}$	[2] Time corresponding to occurrence of $C_{max,ss}$ at steady state
[REDACTED]	[REDACTED]
$AUC_{(0-\tau,ss)}$	[1] AUC over one dosing interval at steady state (Day 7)
[REDACTED]	[REDACTED]
$C_{av,ss}$	[2] Average concentration at steady state (Day 7)
%PTF	[2] Percentage Peak trough fluctuation

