6.3.13.6 Overall Tolerability

Overall tolerability scores will be listed by visit and assessor (patient or investigator) and frequency and percentages will be displayed by overall, treatment and visit and by treatment and race.

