15.3.3 Vital Signs – Physical Findings and Other Relevant Observations Related to Safety

Table 15.3.3:1	Vital Signs (Safety Population)
Table 15.3.3:2	12-Lead Electrocardiogram (Safety Population)

[REDACTED] [REDACTED]

[REDACTED] [REDACTED]

Table 15.3.3:5	Summary of Overall Tolerability (Safety Population)
-----------------------	---

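### Overall tolerability is scheduled only on Day 8, so a subject withdrawn earlier for local intolerance has no rating, and the by-treatment percentages can understate poor tolerability

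*Protocol*

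**What the plan says.** Protocol Table 7-1 (Section 7.2.1) has three entries in the overall tolerability row, one on Day 8 of each period, and an empty follow-up cell. Footnote 23 adds: "Assessment will be done before discharge on the morning of Day 8". The schedule in SAP section 11 has the same row and footnote.

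SAP 6.1.2.7 describes the instrument. Subject and investigator rate independently on a four-point scale ("0 = poor; 1 = fair; 2 = good; 3 = very good"), and on timing the section says: "Assessments will be performed according to the schedule in section 11".

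Protocol 7.3.3 gives two ways in which intolerance can end participation before Day 8. One is mandatory: "Skin irritation of such magnitude that dosing is not possible at IMP application site of the marked thigh during a specific period". The other is optional: "AEs at the discretion of the PI". For withdrawn subjects, "a follow-up visit will be completed for those who were exposed to IMP, within 72 hours of withdrawal/withdrawing from the study".

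Protocol 11.8 only lists the tolerability scores. SAP 6.3.13.6 goes further: "frequency and percentages will be displayed by overall, treatment and visit and by treatment and race". Table 15.3.3:5 is headed for the safety population. SAP 6.3.5 imputes nothing. No denominator is given, and there is no rule for a subject who was dosed but not rated. The visible SAP Addendum does not change this.

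**The concern.** Whether a rating is missing can depend on what the rating would have been. A subject who stops because the product irritates the skin is a likely candidate for the lowest score, and as scheduled is the one not asked.

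There is reason to think the loss could differ between products. Only Test Product 2 contains capsaicin. Protocol 5.1 describes burning, stinging and itching sensations with it, and Protocol 5.3 foresees that the heat effect may be too intense for use to continue. The two diclofenac-only gels do not share that mechanism.

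At stake is how one safety table reads. It could show few or no *poor* ratings for a product while some subjects had left because of that product. In the visible text this is the only scale on which subjects grade overall tolerability themselves.

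**Working it through.** The documents state no tolerability rate and no expected number of intolerance withdrawals, so there is no planned figure to reproduce. What follows is a bound, not an estimate.

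**Inputs**
- N = 48 subjects dosed with a product. Protocol 8.3 randomises 48; this assumes that all reach the product and ignores replacements.
- k = subjects withdrawn for intolerance to that product before Day 8. This is assumed, with range 0 to 6. The top of the range is 48 − 42 = 6, from Protocol 11.2. That is an all-cause allowance for PK evaluability, used here only as a ceiling.
- p = share of rated subjects who say *poor*. This is assumed, at 0% or 10%.
- Each withdrawn subject would have rated *poor*. This is the extreme assumption.

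**Formulas for the percentage *poor***
- Shown, denominator raters: p
- Shown, denominator all dosed: p(N − k)/N
- With the withdrawn counted as *poor*: [p(N − k) + k]/N

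The shortfall is k/N against the all-dosed figure and k(1 − p)/N against the raters figure. For k = 1 and p = 0 both equal 1/48 = 2.08 points.

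| k | p | Shown, raters | Shown, all dosed | Withdrawn counted |
|---|---|---|---|---|
| 0 | 0% | 0% | 0% | 0% |
| 1 | 0% | 0% | 0% | 1/48 = 2.08% |
| 2 | 0% | 0% | 0% | 2/48 = 4.17% |
| 3 | 0% | 0% | 0% | 3/48 = 6.25% |
| 6 | 0% | 0% | 0% | 6/48 = 12.50% |
| 0 | 10% | 10% | 10% | 10% |
| 1 | 10% | 10% | 4.7/48 = 9.79% | 5.7/48 = 11.88% |
| 3 | 10% | 10% | 4.5/48 = 9.38% | 7.5/48 = 15.63% |
| 6 | 10% | 10% | 4.2/48 = 8.75% | 10.2/48 = 21.25% |

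Fractional counts are expected values. The percentage *poor* is too low with either denominator whenever k is above 0, and is undistorted at k = 0.

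**Favourable categories.** Here the unstated denominator matters. Suppose 90% of raters say *good* or *very good* and k = 6. Over raters the table shows 90%. Over all dosed it shows 0.90 × 42/48 = 78.75%. The favourable share is inflated only if raters are the denominator.

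**Crossover.** A subject withdrawn in period 1 or 2 also gives no rating for the products not yet received. That reduces the number rated on those products, but not because of intolerance to them.

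**The case against.** Four objections carry weight.

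1. **Part of the governing text is not public.** Footnote 23 refers to Protocol 9.1.2 and Appendix 15.2. Neither can be read, and the SAP footnote sends the reader to the same places. An empty schedule cell is not conclusive: the physical examination row is marked at screening only, yet Protocol 7.2.7 allows a follow-up examination for subjects withdrawn for an adverse event. An early-withdrawal rule in 9.1.2 therefore cannot be excluded. This stands and lowers confidence. Against it, SAP 6.1.2.7 describes the assessment in full and gives only the schedule for its timing.

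2. **Intolerance is reported elsewhere.** Adverse events are tabulated by product, causality and intensity. Those leading to discontinuation have their own output (Table 15.4.2:3). Disposition includes the primary reason for stopping, and application sites are inspected throughout dosing. An unlabelled row in both schedules also has an entry at follow-up; it may be a dermal score, but that is inference. So a reader who concluded that such withdrawals vanish from the report would be wrong. The cover is incomplete, however. Disposition is tabulated by sequence and overall, not by product. Site inspections are only listed. Under Protocol 12.4, site abnormalities become adverse events only if judged clinically significant. None of these outputs is the subject's own overall rating.

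3. **The bias is conditional.** A reader might infer that the percentages will favour the capsaicin product. The documents do not support that. They give no withdrawal rate for any product, and distortion between products needs such withdrawals both to occur and to differ by product.

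4. **The upper bound is constructed.** A reader might take 12.5 points as a likely error. It puts the whole all-cause allowance on one product for one reason, and a subject who is not evaluable for PK may still have a Day 8 rating.

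**Conclusion.** The gap holds on the visible text. The rating is scheduled on Day 8 only, intolerance can remove a subject before then, and the SAP reports percentages by treatment with no denominator and no line for unrated subjects. The table can therefore understate *poor* ratings for a product with more intolerance withdrawals.

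The size is up to about 2.1 points per such withdrawal, and zero if there are none. This assumes 48 dosed and that each withdrawn subject would have rated *poor*. Any effect on the favourable categories depends on the denominator chosen.

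The importance is minor. The rating is one of the safety variables, which the protocol synopsis classes as other endpoints. It is summarised descriptively with no planned test, and the primary comparison of AUC and Cmax at steady state does not use it. Confidence is moderate because Protocol 9.1.2 and Appendix 15.2 could not be read.

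**What to change.** First check Protocol 9.1.2. If it already provides a rating at early withdrawal, only the SAP change is needed.

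- **Collection.** Take the subject's and the investigator's ratings at withdrawal, or at the follow-up visit already required within 72 hours. Record them against the product in use when the subject stopped. Show them separately from the Day 8 ratings, because they follow fewer doses.
- **Analysis.** In SAP 6.3.13.6, state that the denominator is all subjects dosed with each product. Add a row by product for subjects dosed but not rated, with the reason for discontinuation.

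The cost is one schedule entry at an existing visit and one table row. The SAP itself names an addendum as the route for changes after database lock.

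For subjects already withdrawn without a rating, the row makes the gap visible to the reader. It does not recover the ratings, and it should not be described as removing the bias.
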